6.3.5 CLASI Response

The CLASI is a comprehensive tool for assessment of disease activity and damage in cutaneous lupus, shown to be valid, reliable, and sensitive to changes in disease activity.⁴⁸ Response is defined as 50% improvement from baseline in “A” or “B” scores. This assessment will be applied to all patients as all are required to have cutaneous disease activity.

For the secondary efficacy endpoint of CLASI response at Day 210, patient scores on MAD and POC studies will be compared with baseline for 50% improvement.

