Section	Description of Changes	Rationale
	systems for a total of 2 “B” BILAG body system scores	
	With:	
7	Patients must have at least 1A or 2Bs from the following manifestations of SLE, as defined by the BILAG criteria as modified for use in this study, which must be confirmed by the central data reviewer:	
	a BILAG A or B score in the mucocutaneous body system	
	b BILAG A or B score in the musculoskeletal body system due to active polyarthritis defined as follows:	
	i “BILAG A:” Severe Arthritis, (BILAG item number 41), manifested by observed active synovitis in ≥ 2 joints with marked loss of functional range of movements and significant impairment of basic activities of daily living that has been present on several days cumulatively over the past 30 days , including at the time of the screening visit. See APPENDIX 5 for additional detailed specifications.	
	• Basic ADLs are defined as the following activities which require assistance or assistive devices, (at least 1 must be present and documented in source):	
	○ Ambulation, toileting, grooming- including bathing and dressing; feeding oneself	
	ii “BILAG B:” Moderate Arthritis, Tendonitis or Tenosynovitis, (BILAG item number 42), defined as tendonitis/tenosynovitis, or active synovitis in ≥ 1 joint, (observed or throughout history), with some loss of functional range of movements which lead to some loss of functional range of motion as manifested by effects on instrumental ADLs such as:	
	• Cooking, driving, using the telephone or computer, shopping, cleaning, etc, and has been present on several days over the last 30 days , and is present at the time of the screening visit	
	If only one “B” and no “A” score is present in the mucocutaneous body system or in the musculoskeletal body system due to arthritis, then at least 1 “B” must be present in the other body systems for a total of 2 “B” BILAG body system scores	

Section	Description of Changes	Rationale
Section 5.1, Screening	Add: 
Direct Coomb's test (if indicated for hemolytic anemia)	Text updated to clarity
Section 5.2, Enrollment/Randomization and Day 0 Treatment		
Section 5.3, Treatment Period/Follow-Up Visits		
Section 5.4, Safety Follow-Up Visits		
Section 5.1, Screening	Delete: 
CD4+ count, total IgG and IgM levels, plasma CCI, plasma CCI and CCI whole blood for leukocyte immunophenotype; CCI	Updated to clarify the planned laboratory assessments

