5.4 Inclusion Criteria

Patients who meet the following criteria will be considered eligible to participate in this clinical study:

1. Men and women, ages 18 to 70 years, inclusive
2. Patients must be mentally capable of giving consent and there must be evidence of a personally signed and dated informed consent document indicating that the patient has been informed of all pertinent aspects of the study
3. Patients must have SLE as defined by meeting 4 of the Systemic Lupus International Collaborating Clinics (SLICC) classification criteria for SLE (with at least 1 clinical and 1 immunologic criterion or Lupus nephritis as the sole clinical criterion in the presence of ANA or anti-dsDNA antibodies), either sequentially or simultaneously
4. At screening, patients must have at least 1 of the following:
 - a. Elevated ANA \geq 1:80 via immunofluorescent assay at the central laboratory
 - b. Positive anti-dsDNA or anti-Smith (Sm) above the normal level as determined by the central laboratory
 - c. C3 or C4 below normal as determined by central lab

5. At screening, the SLE Disease Activity Index 2000 (SLEDAI-2K) must be ≥ 6 , including points from at least 1 of the following clinical components:
 - a. Arthritis, rash, myositis, mucosal ulcers, pleurisy, pericarditis, and vasculitis
 - i. Excluding parameters which require central laboratory results: (hematuria, pyuria, urinary casts, proteinuria, positive anti-dsDNA, decreased complement, thrombocytopenia, and leukopenia)
 - ii. Points from lupus headache and organic brain syndrome will also be excluded
6. On Day 0, the SLEDAI-2K must be ≥ 6 , including points from at least 1 of the following clinical components:
 - a. Arthritis, rash, myositis, mucosal ulcers, pleurisy, pericarditis, and vasculitis
 - i. Excluding parameters which require central laboratory results: (hematuria, pyuria, urinary casts, proteinuria, positive anti-dsDNA, decreased complement, thrombocytopenia, and leukopenia)
 - ii. Points from lupus headache and organic brain syndrome are also excluded
7. Patients must have at least 1 of the following manifestations of SLE, as defined by the BILAG criteria as modified for use in this study, which must be confirmed by the central data reviewer:
 - a. BILAG A or B score in the mucocutaneous body system
 - b. BILAG A or B score in the musculoskeletal body system due to active polyarthritis defined as follows:

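### CLASI response is applied to every patient on the ground that all must have skin disease, but the entry criteria do not require it, and a 50% improvement is undefined at a zero baseline.

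*Protocol*

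**What the plan says.** Section 6.3.5 gives the responder rule, "Response is defined as 50% improvement from baseline in" A or B scores, without a minimum baseline value. It then sets the scope: "This assessment will be applied to all patients as all are required to have cutaneous disease activity". The time point follows, with the same threshold: "For the secondary efficacy endpoint of CLASI response at Day 210, patient scores on MAD and POC studies will be compared with baseline for 50%".

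The proportion of patients with a CLASI response is a Phase 2 secondary efficacy endpoint (Appendix 7, Section 2 entry). Section 8.2.4 tests binary secondary endpoints by Pearson's chi-squared on the full analysis set (FAS), and Section 8 sets a two-sided level of 0.10.

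Inclusion criterion 7, in the replacement text recorded in Appendix 7 for Section 4.4, opens with "Patients must have at least 1A or 2Bs from the following manifestations of SLE, as defined by the BILAG criteria". It lists two manifestations: (a) "BILAG A or B score in the mucocutaneous body system" and (b) "BILAG A or B score in the musculoskeletal body system due to active polyarthritis defined as follows". Its closing rule covers a patient with a single B and no A: if that "score is present in the mucocutaneous body system or in the musculoskeletal body system due to arthritis, then at least 1" further B must be found in the other body systems.

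Criteria 5 and 6, read from the Amendment 1 text (its Section 5.4), ask for a SLEDAI-2K of at least 6, "including points from at least 1 of the following clinical components": arthritis, rash, myositis, mucosal ulcers, pleurisy, pericarditis and vasculitis.

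**The concern.** The scope of the endpoint rests on a statement about eligibility that the eligibility criteria do not bear out. A percentage improvement needs a non-zero starting value. If some enrolled patients have no skin activity at Day 0, the responder rule gives no answer for them, yet the text includes everyone.

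A patient with nothing to improve cannot show a treatment effect on this endpoint. Whichever class such patients are put in, they add the same expected share to both arms and shrink the difference between them. The reported proportion would then mix skin response with the mix of patients at entry.

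The response variable is also unclear. The protocol defines A and B only as BILAG grades (Section 6.3.2) and describes CLASI as measuring activity and damage. It does not say which CLASI score is to fall by half.

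**Working it through.** **1. Is skin disease required?** Criterion 7 can be met in these ways:
- a mucocutaneous A or B, with a second B where needed: skin disease present;
- a musculoskeletal A alone: no skin score needed;
- a musculoskeletal B with a B in another body system: the second B need not be mucocutaneous.

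Criteria 5 and 6 need points from at least one of seven components, of which rash is one. No minimum CLASI appears among the criteria. Both earlier full versions of criterion 7 reproduced in the document also accept skin or joint involvement. The reason given in Section 6.3.5 therefore has no support in the criteria.

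**2. The rule at a zero baseline.** Improvement = (baseline − Day 210 score) / baseline. With baseline 0 the denominator is 0, so the rule is undefined.

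**3. The plan's own power figure.** Section 8.1 gives 132 subjects randomised 2:1 (88 and 44), 65% versus 40% on SRI-4, two-sided alpha 0.10, and power above 80%. Power = Φ[(d − 1.645 × SE0) / SE1], with SE0 from the pooled rate and SE1 from the separate rates. This gives 86.6%, so the statement is reproduced. The protocol gives no power figure for CLASI response.

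**4. Size of the dilution.** The documents give neither CLASI response rates nor the share f of patients with baseline 0. Assumed: 50% versus 25% among patients with skin activity, and f from 5% to 30%.
- Zeros as non-responders: rates 0.50(1 − f) and 0.25(1 − f), on 88 and 44.
- Zeros as responders: the same rates plus f, on 88 and 44.
- Restricted: 0.50 and 0.25, on 88(1 − f) and 44(1 − f).

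Under either of the first two, the difference is 25(1 − f) points. Worked at f = 20%:
- Non-responders, 0.40 vs 0.20: pooled rate 0.333, SE0 0.0870, SE1 0.0798; (0.20 − 1.645 × 0.0870) / 0.0798 = 0.712; power 76.2%.
- Responders, 0.60 vs 0.40: pooled rate 0.533, SE0 0.0921, SE1 0.0905; z = 0.536; power 70.4%.
- Restricted, 0.50 vs 0.25 on 70.4 and 35.2: pooled rate 0.417, SE0 0.1018, SE1 0.0942; z = 0.877; power 81.0%.

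| Share f | Difference, all FAS | Zeros non-responders | Zeros responders | Restricted (N) |
|---|---|---|---|---|
| 5% | 23.75 points | 85.7% | 84.1% | 86.8% (125) |
| 10% | 22.5 points | 82.8% | 79.7% | 85.0% (119) |
| 20% | 20 points | 76.2% | 70.4% | 81.0% (106) |
| 30% | 17.5 points | 68.5% | 61.1% | 76.0% (92) |

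Against restriction, the loss at 5% is 86.8 − 85.7 = 1.1 to 86.8 − 84.1 = 2.7 points. At 30% it is 76.0 − 68.5 = 7.5 to 76.0 − 61.1 = 14.9 points.

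**5. Other rates.** With the SRI-4 rates (65% versus 40%) used in place of the assumed CLASI rates, restriction is again best: by between 1 and 2 points at 5%, and by about 9 to 12 at 30%.

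**The case against.** Several points can be made for the plan.

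- **Entry with arthritis alone.** A reader might infer that such patients can enrol. The documents do not show this. SLEDAI-2K must be at least 6, and the item weights that would settle whether arthritis alone reaches 6 are not given. What stands is narrower: no qualifying skin score is required.
- **Joint-route patients and a zero CLASI.** A reader might also infer that everyone entering by the joint route scores 0. That does not follow. BILAG grade C covers mild disease, so a patient without a mucocutaneous A or B may still score on CLASI. Only the zero-baseline subset is affected, and it may be small.
- **Meaning of the sentence.** It could mean only that the instrument is administered to everyone, and no text says how zero baselines are to be classed. Section 8.2.4 leaves missing-data handling to the SAP, which was not available. This is fair as regards handling. It does not rescue the stated reason, and a SAP that restricted the denominator would sit badly with a protocol that applies the endpoint to all.
- **Skin effect elsewhere.** Change from baseline in CLASI is a separate secondary endpoint and is defined at a zero baseline. It would be too strong to say the trial cannot describe skin effect.
- **A or B.** If BILAG grades are meant, a baseline A or B is presupposed and the zero-baseline problem recedes. The wording is ambiguous rather than demonstrably wrong, and a clarification would settle it.

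Finally, the current Section 4.4 was not in the part of the protocol at hand. Criterion 7 is taken from the replacement text in Appendix 7. Criteria 5 and 6 come from Amendment 1, for which the Amendment 2 log shows only a wording edit to criterion 6.

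**Conclusion.** The point holds in limited form. The reason for applying CLASI response to everyone contradicts the inclusion criteria, and the responder rule is undefined for any enrolled patient with a baseline score of 0. This is a wrong statement in the protocol, not detail properly left to the SAP.

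The consequence is dilution of one secondary endpoint if zero-baseline patients are classed either way in the FAS. Its size cannot be fixed from the documents. On the assumed 50% versus 25%, it runs from about 1 to 3 power points at a 5% zero share to about 7 to 15 at 30%. Restriction gave the higher power at every share and both sets of rates examined, despite fewer patients. The primary SRI-4 analysis and the sample size are untouched.

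**What to change.** In Section 6.3.5, delete the sentence giving the reason for including all patients. Replace the A or B wording with the CLASI activity score. Define response as a reduction of at least 50% in that score at Day 210, analysed in patients with a prespecified non-zero baseline activity score. Summarise CLASI values, including any new activity, separately in the remaining patients.

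The baseline cut-off should be fixed before unblinding. Any value above 0 is the simplest choice but lets a fall from 1 to 0 count as a full response, so the sponsor may prefer a higher minimum.

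The cost is a smaller denominator: about 125 of 132 at a 5% zero share, 92 at 30%. The change also settles the response variable and the analysis population for this endpoint, so it is more than an editorial correction and belongs in an amendment with a matching SAP entry. No new assessment is needed, since the schedule in the Amendment 1 text already collects CLASI at Day 0 and Day 210.

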Section	Description of Changes	Rationale

PROTOCOL SUMMARY, Main Criteria for Inclusion and Exclusion (inclusion criterion 7, sub-bullets a and b)
	
Replace:
 
7 Patients must have at least 1 of the following manifestations of SLE, as defined by the BILAG criteria as modified for use in this study, which must be confirmed by the central data reviewer:
 
 a. BILAG A or B score in the mucocutaneous body system b. BILAG A or B score in the musculoskeletal body system due to active polyarthritis as defined in the protocol Section 4.4. c. If only one “B” and no “A” score is present in the mucocutaneous body system or in the musculoskeletal body system due to arthritis, then at least 1 “B” must be present in the other body systems for a total of 2 “B” BILAG body system scores 
With:
 
7 Patients must have at least 1A or 2Bs from the following manifestations of SLE, as defined by the BILAG criteria as modified for use in this study, which must be confirmed by the central data reviewer:
 
 a. BILAG A or B score in the mucocutaneous body system b. BILAG A or B score in the musculoskeletal body system due to active polyarthritis as defined in the protocol Section 4.4. 
If only one “B” and no “A” score is present in the mucocutaneous body system or in the musculoskeletal body system due to arthritis, then at least 1 “B” must be present in the other body systems for a total of 2 “B” BILAG body system scores
	
Text updated to clarify that a minimum BILAG 1 ‘A’ or 2 ‘B’ scores is required for screening

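### CLASI response is scored in every patient on the stated ground that all must have skin disease, but the entry criteria do not require skin disease, so a 50% improvement can be undefined for some FAS patients

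*Protocol*

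**What the plan says.** Section 6.3.5 of the protocol defines the endpoint and its population. "Response is defined as 50% improvement from baseline", with no minimum baseline score and no rule for a baseline of zero. On who is scored it says: "This assessment will be applied to all patients as all are required to have cutaneous disease activity". CLASI response at Day 210 is a Phase 2 secondary efficacy endpoint. Section 8.2.4 tests binary secondary endpoints with Pearson's chi-squared on the FAS, and Section 8.2.3 applies the 2-sided 0.10 criterion of the primary endpoint to secondary endpoints as well.

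The current wording of inclusion criterion 7 is given as replacement text in Appendix 7 (entry for Section 4.4): "Patients must have at least 1A or 2Bs from the following manifestations of SLE". Two manifestations follow as separate items. One is "BILAG A or B score in the mucocutaneous body system"; the other is "BILAG A or B score in the musculoskeletal body system due to active polyarthritis defined as follows". The Protocol Summary entry has the same structure. A closing sentence covers the patient with a single B and no A, where that B "score is present in the mucocutaneous body system or in the musculoskeletal body system due to arthritis", and asks for one more B among the other body systems.

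**The concern.** The reason given for scoring everyone is a statement about eligibility, and the eligibility rule does not bear it out. Skin disease is one route into the trial, not a condition of entry. A patient who enters through the joints can have a baseline CLASI activity score of 0.

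For that patient there is nothing to improve by half. If response is programmed as a Day 210 score no more than half of baseline, a patient who stays at 0 responds automatically, since 0 ≤ 0. If it is programmed as percent change, the patient can never respond. Neither result says anything about treatment. Such patients dilute the comparison, and the response rates reported in both arms then depend partly on a coding choice.

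**Working it through.** **1. Is there a route into the trial without skin disease?**

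| Entry rule | What it asks | Is skin disease needed? |
|---|---|---|
| Criterion 7, one A | mucocutaneous A or musculoskeletal A | No: a musculoskeletal A suffices |
| Criterion 7, single B | a mucocutaneous or arthritis B, plus a B in another system | No: an arthritis B plus a non-skin B suffices |
| SLEDAI-2K (V2.0 Section 5.4; the V3.0 section is not shown) | score of at least 6, with points from at least one listed component | No: arthritis and rash are alternatives |

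None of these rules supplies the requirement that Section 6.3.5 relies on. The older full texts in the file (V2.0 and V1.0) have the same mismatch, so the log's revision of criterion 7 did not create it.

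**2. The plan's own power figure.** Section 8.1 states more than 80% power for SRI-4 with 132 patients at 2:1 (88:44), 65% vs 40%, 2-sided 0.10. Exact enumeration of the chi-squared test gives 86.3%, so the statement holds and is not in dispute. The protocol states no power for CLASI response.

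**3. Effect of zero-baseline patients.** Let f be the share of the FAS with a baseline CLASI activity score of 0, and p the response rate among the rest.

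- Zeros as non-responders: rate = p(1 − f).
- Zeros as responders (assuming they stay at 0): rate = p(1 − f) + f.
- Under either coding, difference = (p_active − p_placebo)(1 − f).
- Restricted to baseline above 0: the difference is unchanged, and the arms shrink to about 88(1− f) and 44(1− f).

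The documents give neither f nor CLASI response rates. I assume 55% vs 30% among patients with skin activity and show a range of f. Power is by exact enumeration of Pearson's chi-squared at 2-sided 0.10, with 88:44 for the full FAS.

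| f | Difference, full FAS | Power, zeros as non-responders | Power, zeros as responders | Power, restricted (n per arm) |
|---|---|---|---|---|
| 5% | 25 × 0.95 = 23.75 points | 84% | 83% | 85% (84:42) |
| 10% | 25 × 0.90 = 22.5 points | 81% | 79% | 83% (79:40) |
| 20% | 25 × 0.80 = 20 points | 74% | 71% | 81% (70:35) |
| 40% | 25 × 0.60 = 15 points | 58% | 54% | 70% (53:26) |

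**4. Effect on the reported placebo rate.** At f = 20% it is 0.30 × 0.80 = 24% with zeros as non-responders, or 24% + 20% = 44% as responders. At f = 40% it is 0.30 × 0.60 = 18%, or 18% + 40% = 58%. Only the coding differs.

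**5. Sensitivity to the assumed rates.** Borrowing 65% vs 40% from SRI-4, with a normal approximation, gives at f = 20% power of 71% (non-responders), 73% (responders) and 79% (restricted). The two codings change places, but the restricted analysis still has the highest power.

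**The case against.** The strongest reply is that handling of a zero baseline belongs in the SAP. Sections 8 and 8.2.4 send data handling and secondary-endpoint details there, and the SAP is not shown. That is fair for the coding rule, and a SAP that restricts the evaluable set would remove the practical consequence. It would not make the sentence in Section 6.3.5 true. That sentence fixes the population, so a SAP restriction would have to contradict it.

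The size of the problem is also open to challenge, and this part stands. A reader might infer that every patient without a mucocutaneous A or B has a CLASI of 0. The documents do not support that. Section 6.3.2 describes BILAG C as mild stable disease, so a patient who enters on arthritis may still have a low non-zero CLASI. Nor is arthritis alone always enough: that holds for a musculoskeletal A, whereas an arthritis B needs a second B, which may itself be mucocutaneous. At shares of 5 to 10% the power loss against the restricted analysis is only about 2 to 4 points.

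Two further inferences are tempting and do not hold. One is that change from baseline in CLASI should be restricted in the same way. Change from zero is well defined, and excluding those patients would discard new skin disease arising on study. The other is that the mention of MAD scores in Section 6.3.5 must go because Section 8 limits testing to Phase 2. That sentence compares scores with baseline, and Section 8 provides descriptive summaries for each phase.

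**Conclusion.** The point holds for the responder endpoint. Section 6.3.5 rests its population rule on a requirement that the entry criteria do not contain. Followed as written, it can put patients with no skin activity into a 50%-improvement endpoint where their outcome is undefined or set by coding.

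The contradiction can be read directly from the text; its size cannot. Under the assumed 55% vs 30%, the loss against a restricted analysis runs from 1 to 2 points of power at f = 5% to 12 to 16 points at f = 40%. The true f is unknown and may be at the low end. It would be wrong to infer that the trial's main result is at risk: the primary SRI-4 analysis does not use CLASI. The correction is worth making because a secondary endpoint would otherwise rest on a false premise and because it costs little.

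**What to change.** Delete the sentence in Section 6.3.5 that says all patients must have cutaneous activity. Define CLASI response in FAS patients with a Day 0 CLASI activity score above 0, compared by randomised arm. The restriction uses a value measured before treatment, so the randomised comparison within that subset is preserved. Because a baseline of 1 needs only a one-point fall, add a higher prespecified minimum score as a sensitivity analysis. Keep change from baseline in CLASI on the full FAS, and leave the descriptive scoring of MAD patients as it is.

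The cost is wording in the protocol, matched in the SAP. The V2.0 schedule already collects CLASI on Day 0, so no new data are needed. The downside is a smaller denominator for one secondary endpoint.

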6.3.6 ACR-28 Joint Count

The ACR-28 joint count will evaluate the number of tender and swollen joints in the shoulder, elbow, wrist, hand, knee joints. Joints of the feet are excluded.

